The favorable results on the primary endpoint in the alteplase 0.6/0.04 mg/kg dosing group were supported by similar trends for other prespecified analyses, including sensitivity analyses of the primary endpoint, as well as secondary efficacy endpoints of lower all-cause mortality and lower all-cause mortality or mechanical ventilation up to Day 28 compared with the SOC group, greater improvement in median $\text{PaO}_2/\text{FiO}_2$ ratio from baseline to Day 6 and more ventilator-free days from the start of treatment to Day 28 than in the alteplase 0.3/0.02 mg/kg and SOC groups.

A Kaplan-Meier estimate of the unadjusted primary analysis showed a separation of the alteplase 0.6/0.04 mg/kg group compared with the other two treatment groups, beginning at approximately Day 11. The risk difference for the alteplase 0.6/0.04 mg/kg group compared with the SOC group at Day 28 was 19.1% in favour of alteplase (95% CI -10.6%, 48.8%).

[REDACTED]

Secondary and further endpoint results supported the clinical benefit of alteplase in addition to SOC, particularly for the alteplase 0.6/0.04 mg/kg group. Both alteplase groups had numerically fewer cases of all-cause mortality than in the SOC group at Day 28. All-cause mortality or mechanical ventilation at Day 28 was considered as treatment failure; both alteplase groups had fewer cases of all-cause mortality or mechanical ventilation at Day 28 than the SOC group. The alteplase 0.6/0.04 mg/kg group had more ventilator-free days from the start of treatment to Day 28 than the alteplase 0.3/0.02 mg/kg and SOC groups. In addition, the alteplase 0.6/0.04 mg/kg group had a greater improvement in median $\text{PaO}_2/\text{FiO}_2$ ratio from baseline to Day 6 compared with the alteplase 0.3/0.02 mg/kg or SOC group..

[REDACTED]

Safety

The overall safety results were generally comparable across the treatment groups. Patients treated with alteplase and those receiving only standard of care had similar frequencies of any adverse events (AEs), severe AEs, and serious AEs. The majority of reported AEs were of mild or moderate intensity. No new safety signals were identified.

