2.1.3 Secondary endpoints

The following secondary endpoints to assess safety and efficacy in this setting have been evaluated in Part 1:

- All cause mortality at Day 28
- Number of ventilator-free days from start of treatment to Day 28
- Improvement of Sequential (sepsis-related) Organ Failure Assessment (SOFA) score by ≥ 2 points from baseline to end of Day 6
- Major bleeding events (MBE) (according to International Society on Thrombosis and Haemostasis [ISTH] definition [R05-0344](#) until Day 6, see [Section 5.2.5.1](#)).
- Daily average $\text{PaO}_2/\text{FiO}_2$ ratio (or inferred $\text{PaO}_2/\text{FiO}_2$ ratio from SpO_2) change from baseline to Day 6
- All-cause mortality or on mechanical ventilation at Day 28

In Part 2, the following key secondary endpoints will be evaluated:

- Treatment failure defined as all cause mortality or mechanical ventilation at Day 28
- All cause mortality at Day 28

[figure not shown]
In Part 2, the following secondary endpoints will be evaluated:

[figure not shown]
Clinical Trial Protocol

Page 33 of 140

Proprietary confidential information © 2022 Boehringer Ingelheim International GmbH or one or more of its affiliated companies

- Number of oxygen-free days up to Day 28
- Length of hospital stay up to Day 28
- Major bleeding events (MBE) (according to International Society on Thrombosis and Haemostasis [ISTH] definition [[R05-0344](#)]) until Day 6, see [Section 5.2.5.1](#).
- PaO₂/FiO₂ ratio (or inferred PaO₂/FiO₂ ratio from SpO₂) change from baseline to Day 6

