7.5 DETERMINATION OF SAMPLE SIZE

Part 1 of the study plans to randomise approximately 60 patients in total, with a view to exploring the data in a descriptive manner.

Sample size considerations are limited to Part 2 and the NIV patient cohort.

Part 2 has a planned confirmatory analysis at the 2-sided type I error level of alpha=5% with a power of 85% to 90%, applicable to the first two steps within the pre-planned hierachial testing procedure. The trial uses a randomisation allocation ratio of 2:1, which leads to approximately 140 NIV patients on the treatment arm and approximately 70 NIV patients on the SOC alone.

With regard to the primary analysis of the primary endpoint, H0_1 in the hierarchy testing procedure, in the NIV patient cohort, a hazard ratio of 2.0 is assumed, with event rates in the SOC alone group and alteplase group of approximately 30% and 50%. In the alteplase arm, it is expected to have a median time to event of 20 to 30 days.

With regard to the primary analysis of the key secondary endpoint “Treatment failure at Day 28”, H0_2 in the hierarchy testing procedure, in the NIV patient cohort, a risk difference of -20% is assumed, with event rates in the SOC alone group and alteplase group of approximately 40% and 20%.

With regard to the primary analysis of the key secondary endpoint “All cause mortality at Day 28”, H0_3 in the hierarchy testing procedure, in the NIV patient cohort, there would be a power of 85% under the assumptions of a risk difference of -16%. This would be with event rates in the SOC alone group and alteplase group of approximately 25% and 9%. These are very similar event rates as observed in Part 1.

The sample size determination or justification is in line with the null hypotheses and hierachial testing approach as defined in [Section 7.1](#), whereby it is planned to test for superiority of alteplase vs SOC alone in the NIV patient cohort. Whilst the assumptions are still rather approximate, the magnitude of these assumptions is similar to the available results

in other COVID-19 patients [[R20-2001](#), [R20-2246](#)] and to the results observed in Part 1 of this study. In this emerging disease and during this pandemic, standard of care is evolving, and other factors are having an influence, for example, the introduction of vaccines.

Calculations were performed using the software R Version 3.6.1 and nQuery Version 4.0.

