4. CHANGES IN THE PLANNED ANALYSIS OF THE STUDY

Whilst in the CTP there is a reference to the determination of the Per Protocol Set (PPS), this will only be done for Part 2 of the study. This is not considered to be a change from the protocol, since it will be done for Part 2. This is considered to be a clarification.

Regarding the protocol definition of the primary endpoint, time to clinical improvement or hospital discharge, there has been no detail added regarding patients potentially discontinuing the study early due to withdrawal of consent. In the unlikely event that a patient does discontinue from the study due to withdrawal of consent, prior to being able to determine if he had clinical improvement or hospital discharge, or had intake of bail-out therapy or death, he will be censored at the time of withdrawal. This is not considered to change the protocol definition, rather a clarification.

The randomisation stratification factor baseline ventilation status (Non Invasive Ventilation (NIV) / Mechanical Ventilation (MV)) is correlated with the baseline status on the world health organisation (WHO) eleven-point clinical progression scale (5, 6, 7, 8 or 9). That is to say, NIV take on values of 5 and 6, whilst MV takes on values of 7, 8 and 9 on the WHO clinical progression scale. Only the randomisation stratification factor ventilation status will be used in the primary model to avoid over parameterising. This is not considered to be a change from the protocol, since this still includes the baseline WHO status.

The secondary endpoint Improvement of Sequential (sepsis-related) Organ Failure Assessment (SOFA) score by ≥ 2 points from baseline to end of Day 6 is to be determined based upon assessments at Day 6 / hospital discharge. This is not considered to change the protocol definition, rather a clarification.

In [Section 6.7](#) the definition of ‘on treatment’ has been modified, but is not inconsistent with the CTP. That is to say, alteplase ‘on treatment’ starts from first administration of alteplase and ends 288 h later, or longer for patients with more than 5d of infusion. For the SOC group, ‘on treatment’ starts from randomization and ends 288 h later.

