If the patient has an MBE, at any timepoint up to end of Day 6 then he has met this unfavorable endpoint. If it is unknown whether the patient had an MBE up to end of Day 6, regardless of the reason, then it will be assumed that the patient did not have an MBE by the end of Day 6. This is a safety defined endpoint and the starting point for consideration should be consistent with the 'on treatment' definition in [Section 6.7](#), however only including events up to midnight of Day 6.

ACM at Day 28, FAS, binary endpoint

If it is unknown whether the patient was dead at end of Day 28, then it will be assumed that the patient did not die up to Day 28, regardless of the reason. This unfavorable endpoint is met if:

- the last known status of the patient is 10 on the WHO clinical progression scale by the end of Day 28, or
- vital status is dead within 28 days

ACM / MV at Day 28, FAS, binary endpoint

If it is unknown whether the patient was on MV at Day 28, it will be assumed that the patient was not on MV at Day 28, regardless of the reason. This unfavorable endpoint is met if:

- the last known status of the patient has a value of ≥ 7 on the WHO clinical progression scale, up to end of Day 28, or
- vital status is dead within 28 days

Daily average PaO₂/FiO₂ ratio (or inferred PaO₂/FiO₂ ratio from SpO₂) change from baseline to Day 6, FAS, continuous endpoint

This assessment is to be measured approximately 3-times daily on each of days 0 to 7, and again on day 28, but only whilst the patient is still in hospital. All available values on each of these days, regardless of the position of the patient when being measured, will be averaged in order to determine the daily average PaO₂/FiO₂ ratio for that patient. The higher the value the better the health status of the patient.

[figure not shown]
- If the patient is still in hospital during day 6 then the day 6 daily average value will be used, if available.
- If the patient has been discharged from hospital prior to day 6 then the daily average at the time of hospital discharge will be used as a surrogate for day 6, if available.
- If the patient has died prior to day 6 then there will be no imputation but the death handled as failure in the determination of the difference in medians and 95% CI.

[figure not shown]
Based upon this, the change from baseline for each patient will be calculated and used for the analysis.

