6.3 SUBJECT SETS ANALYSED

The subject sets as defined in protocol Section 7 for the Randomised Set (RS), Full Analysis Set (FAS) and Treated Set (TS) will be used.

The Screened set (SCR), not outlined in the CTP, will include all patients screened.

The RS will consist of all randomised patients.

The FAS will consist of all randomised patients with at least one baseline and one post baseline assessment relating to the primary endpoint of interest. That is to say, they need to have at least one assessment post baseline on the 11-point WHO Clinical Progression Scale.

The TS will consist of all patients who were randomised and, for patients in the alteplase groups, treated with at least one dose of trial drug.

The Pharmacokinetic set (PKS), not outlined in protocol, will comprise all subjects in the TS who provided at least one PK endpoint and had no important protocol violations relevant to the evaluation of PK.

Table 6.3: 1 Subject sets analysed

Class of endpoint	Subject set			PKS
	SCR / RS	TS	FAS	
Primary endpoint			primary and supplementary analyses	
Secondary and further EFFICACY endpoints			X	
Secondary and further SAFETY endpoints		X		
Treatment exposure		X		
Disposition	X			
Demographic/baseline		X	X	
Concomitant medications and compliance		X	X	
All other safety analyses		X		
PK analyses				X

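### In the Part 1 SAP, a patient last seen ventilated (WHO 7–9) whose Day 28 status is unknown is scored both as a non-failure and as a failure on death or mechanical ventilation at Day 28

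*SAP*

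**What the plan says.** Protocol section 2.1.3 lists the Part 1 secondary endpoint as "All-cause mortality or on mechanical ventilation at Day 28" and gives no rule for unknown status.

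SAP (Part 1) section 5.2.2, under ACM / MV at Day 28, adds two rules in succession:

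- **Rule 1 (unknown status):** when ventilation status at Day 28 is unknown, "it will be assumed that the patient was not on MV at Day 28, regardless of the reason".
- **Rule 2 (criterion):** the unfavourable endpoint is met if "the last known status of the patient has a value of ≥ 7 on the WHO clinical progression scale" up to the end of Day 28, or if vital status shows death within 28 days.

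Section 4 of the same SAP fixes what the scores mean: "MV takes on values of 7, 8 and 9 on the WHO clinical progression scale". Section 6.6, on missing data, has specific rules for PaO₂/FiO₂, SOFA and APACHE II but none for this endpoint.

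SAP (Part 2) section 5.2.1 defines the corresponding key secondary endpoint by the last-known-status and vital-status criteria alone. The sentence that assumes no ventilation is not there.

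**The concern.** Rule 1 is a favourable imputation. Rule 2 carries the last observed status forward. For a patient who leaves observation while ventilated they give opposite answers, so the classification depends on which sentence the programmer followed. Rule 1 also treats as ventilation-free the patients who were sickest when last seen.

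The Part 1 result on this endpoint was used. Protocol section 1.1 says "All-cause mortality or mechanical ventilation at Day 28 was considered as treatment failure" and reports fewer cases in both alteplase groups than under standard of care, as support for clinical benefit. A pre-specified binary endpoint cited in that way should give one answer per patient. The direction of any effect is not known in advance: Rule 1 flatters whichever arm holds the affected patient.

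**Working it through.** The plan states no figure to reproduce here. The check applies both rules to every relevant patient type and then sizes one reclassification.

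**Step 1. Apply both rules to a patient not known to be dead, with Day 28 status unknown.**

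| Last known WHO score | Rule 1 | Rule 2 | Agree? |
|---|---|---|---|
| 4, 5 or 6 | non-failure | non-failure | yes |
| 7, 8 or 9 | non-failure | failure | **no** |

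Known deaths are failures under both rules through vital status. The conflict is therefore limited to a last score of 7, 8 or 9.

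**Step 2. Look for a precedence rule.**

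- *Rule 1 applies only when there is no last known status.* The endpoint is analysed on the FAS, and section 6.3 says of FAS patients that "they need to have at least one assessment post baseline on the 11-point WHO Clinical Progression Scale". A last known status therefore always exists, and on this reading Rule 1 would never be used.
- *Rule 1 overrides Rule 2.* Carrying the last status forward would then do nothing for patients without a Day 28 status.
- *Vital status decides.* It shows death, not ventilation.
- *Another section decides.* Section 6.6 does not cover the endpoint. For ventilator-free days, section 5.2.2 sets a patient who withdrew consent before Day 28 to missing (zero if known dead at Day 28), which is a third treatment of the same patient.

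The mortality paragraph just above uses the same form of words without conflict, because death cannot reverse. Ventilation status can.

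**Step 3. Size of one reclassified patient.**

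Inputs: about 20 patients per arm (protocol synopsis). For standard of care, protocol section 1.1 reports 9 patients as 40.9% and 11 patients as 50.0%, so n = 9 / 0.409 = 22.0 and n = 11 / 0.500 = 22.

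Shift in the crude arm rate = 100 / n:

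- n = 20: 100 / 20 = 5.0 percentage points
- n = 22: 100 / 22 = 4.5 percentage points

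The 22 comes from adverse-event percentages; the FAS denominator could differ slightly. The planned estimate is a risk difference from a logistic model adjusted for ventilation type and age, so its shift would be close to the crude figure but not identical.

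**The case against.** The strongest reply is that Rule 1 is only a loosely worded default for patients with no Day 28 observation. The main such group is patients discharged before Day 28, for whom section 6.6 says only vital status is collected afterwards. Provided their last score is 6 or less, both rules make them non-failures, so Rule 1 would be redundant rather than contradictory. This explains how the sentence may have arisen, but it does not remove the conflict. Rule 1 applies regardless of the reason and makes no exception for a patient last seen ventilated.

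Other parts of the reply stand:

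- The affected group is small and may be empty. WHO status is recorded daily in hospital, and section 4 of the Part 1 SAP calls withdrawal of consent unlikely.
- Part 1 is exploratory and already reported. The interim report is dated 14 September 2021, and Global Amendment 3 refers to a final database lock. Editing the SAP text cannot change the conduct of Part 1.

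A reader might also infer more than the documents support:

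- *That the confirmatory test of treatment failure is affected.* It uses Part 2 patients only, under the Part 2 SAP, which has the single last-known-status rule.
- *That the conflict enters the planned pooled analysis.* SAP (Part 2) section 3 says that analysis uses endpoints as defined in Part 2, so the disputed sentence does not apply.
- *That one patient is worth a quarter of the effect assumed for Part 2.* Protocol section 7.5 says "a risk difference of -20% is assumed, with event rates in the SOC alone group and alteplase group of approximately 40% and 20"%, but for the non-invasive ventilation cohort only. The 5-point shift is for whole Part 1 arms, which mix non-invasive and invasive ventilation, so the ratio compares unlike populations. Section 7.5 also calls its assumptions approximate and rests them on other COVID-19 results as well as Part 1. Its statement that rates are very similar to Part 1 concerns mortality.

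**Conclusion.** The rule is wrong as written, within a narrow scope. For a patient not known to be dead, with Day 28 ventilation status unknown and a last known WHO score of 7 to 9, SAP (Part 1) section 5.2.2 gives two incompatible outcomes and no precedence. Each such patient would move a crude Part 1 arm rate by 5.0 points (n = 20) or 4.5 points (standard of care, n = 22).

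This rests on the literal wording of both rules and on arm sizes taken from the protocol. The number of affected patients is not given and may be zero, so the documents do not show that any reported Part 1 figure is in error. The Part 2 confirmatory analysis and the planned pooled analysis are unaffected.

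**What to change.** - Delete the sentence that assumes no ventilation, or limit it to patients whose last known WHO score is 6 or less and who have no recorded death. Either change brings Part 1 into line with the Part 2 SAP. As Part 1 is complete, this can be recorded as a clarification in the trial report.
- Confirm which rule the Part 1 derivation used.
- Report the number of patients per arm whose class depends on the choice.
- Re-derive the Part 1 estimate behind the protocol section 1.1 statement only if that number is not zero.

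The cost is one sentence, one check of the derivation program and one line in the report. If patients are affected and Rule 1 was programmed, the failure rate in their arm will rise.

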6. GENERAL ANALYSIS DEFINITIONS

6.1 TREATMENT(S)

For the purposes of the statistical analyses, treatments will be referred to in the same context as in Section 7.4 of the protocol.

- “Alteplase low”, which is alteplase 0.3mg/kg over 2 hours followed by 0.02 mg/kg/h over 12 hours
- “Alteplase high”, which is alteplase 0.6 mg/kg over 2 hours followed by 0.04 mg/kg/h over 12 hours
- Standard of Care (SOC)

Alteplase treatment is planned to be up to end of Day 5 but all patients should be taking SOC in the background. On day 1 there is an initial 2 h infusion for all, followed up by a longterm 12 h infusion. On days 2-5 the patients can receive an optional 2h infusion (based on investigator decision), but only on one of these days. Each patient should receive a longterm 12h infusion on these remaining 4 days.

6.2 IMPORTANT PROTOCOL DEVIATIONS

Whilst it is not planned to conduct a Per Protocol analysis for Part 1 of this study (too few patients), patients with any of the following important protocol deviations (iPDs) will be reviewed on a case by case basis (2) and (3). The review of the iPDs will be used to determine criteria for a PPS for Part 2 of the study.

Note that this is a working list and may be updated again prior to the final Report Planning Meeting (RPM) prior to the snapshot related to end of Part 1. Inclusion criteria/exclusion criteria numbers refer to the definition given in the protocol or CRF.

Table 6.2: 1 Handling of iPDs

iPD code	iPD Category & Brief Description
A	Entrance Criteria Not Met
A1	Inclusion Criteria not met
A1.1	Patient too young (IC1)
A1.2	Diagnosis of ARDS questionable (IC2,4,5)
A1.3	Patient does not test positive for SARS-CoV-2 (IC3)
A2	Exclusion Criteria not met
A2.1	Patient has baseline conditions that are not permitted for safety reasons (EC1-31)

Table 6.2: 1 Handling of iPDs (continued)

A2.2	Patient has baseline conditions that prevent patient from complying with study protocol (EC1-31)
A2.3	Patient has had previous conditions or procedures that are not permitted (EC1-31)
A2.4	Patient has had forbidden previous therapy (EC1-31)
A2.5	Patient pregnant (EC25)
B	Informed Consent
B1	Informed consent not available (IC6)
B2	Informed consent not signed at screening visit 1 (IC6)
B3	Informed consent not available or not available at visit 2a (pre-dose) (IC6)
C	Trial medication and randomisation
C1	Method of assigning patients to treatment arms
C1.1	Randomisation not followed according to protocol
C1.2	Patients do not receive the initial treatment they were randomised / allocated to
C1.3	Patient assignment not followed
C1.4	Timeframe > 1 day between randomisation and first drug intake
C2	Non-compliance
C2.1	Overall Compliance not between 80% and 120% inclusive – see definition in Section 5.4 .
C2.2	Patient takes the optional 2h infusion on more than one occasion after the initial 2 h infusion.
C3	Drug assignment and administration of doses for each patient
C3.1	Dosage and treatment schedule not given according to protocol for initial iv infusion
C3.2	Dosage and treatment schedule not given according to protocol for long term iv infusion
C3.3	Drug not permanently discontinued according to Section 3.3.4.1 of CTP
C3.4	Drug not temporarily interrupted according to Section 3.3.4.1 of CTP

Table 6.2: 1 Handling of iPDs (continued)

D	Concomitant medication
D1	Intake of restricted concomitant medication according to protocol section 4.2.2.1 and Section 9.2
D2	Intake of marketed Actilyse® (non-study drug) not as ultima-ratio or bail-out
G	Other trial specific important deviations
G1	Other protocol violations affecting patient rights or safety (manual PDs to be captured)

6.3 SUBJECT SETS ANALYSED

The subject sets as defined in protocol Section 7 for the Randomised Set (RS), Full Analysis Set (FAS) and Treated Set (TS) will be used.

The Screened set (SCR), not outlined in the CTP, will include all patients screened.

The RS will consist of all randomised patients.

The FAS will consist of all randomised patients with at least one baseline and one post baseline assessment relating to the primary endpoint of interest. That is to say, they need to have at least one assessment post baseline on the 11-point WHO Clinical Progression Scale.

The TS will consist of all patients who were randomised and, for patients in the alteplase groups, treated with at least one dose of trial drug.

The Pharmacokinetic set (PKS), not outlined in protocol, will comprise all subjects in the TS who provided at least one PK endpoint and had no important protocol violations relevant to the evaluation of PK.

Table 6.3: 1 Subject sets analysed

Class of endpoint	Subject set			PKS
	SCR / RS	TS	FAS	
Primary endpoint			primary and supplementary analyses	
Secondary and further EFFICACY endpoints			X	
Secondary and further SAFETY endpoints		X		
Treatment exposure		X		
Disposition	X			
Demographic/baseline		X	X	
Concomitant medications and compliance		X	X	
All other safety analyses		X		
PK analyses				X

